2. In Pharmacy: Product Supply, Distribution, and Accountability (Section 5.3), the following changes are made to allow sites the option to use locally available depot medroxyprogesterone acetate (DMPA) instead of study-provided DMPA:
 - a. The following paragraph is added as the 3rd paragraph in Section 5.3.1

Sites may use locally available DMPA if drug importation issues or delays are anticipated or encountered. The locally available DMPA must be approved by the A5338 Core Team before it can be used for the study. No additional funding will be provided to sites for purchasing DMPA locally, and participants and the participants' insurers must not be billed for the product.
 - b. Section 5.3.2

The site pharmacist is required to maintain complete records of all study products received from the NIAID CRPMC **or any other source** and subsequently dispensed. ~~All unused study products must be returned to the NIAID CRPMC (or as otherwise directed by the sponsor).~~ **Study product not obtained from the CRPMC should be disposed of in accordance with the disposal standard operating procedures at the site** after the study is completed or terminated. The site pharmacist at non-US Clinical Research Sites (CRSs) must follow the instructions in the manual *Pharmacy Guidelines and Instructions for DAIDS Clinical Trials Networks* in the section Study Product Management Responsibilities **for the destruction of unused study products obtained from the CRPMC.**
3. In the noncompliance criteria for premature study discontinuation (Section 8.1), the following changes are made to clarify the criteria for missed doses and pharmacokinetic (PK) sampling:

a. Section 8.1.3

Missed 2 or more of the RIF and/or EFV doses within one week prior to PK sampling at week 2, 4, 6, or 8 and did not return with acceptable adherence (ie, missed 2 or more of the RIF and/or EFV doses) for the rescheduled PK sampling for 2 consecutive study weeks.

b. Section 8.1.4

Missed 2 or more of the RIF and/or EFV doses within one week prior to PK sampling at week 10 or 12 and did not return with acceptable adherence (ie, missed 2 or more of the RIF and/or EFV doses) for the rescheduled PK sampling.

4. In Section 9.5, the following changes are made to add review by an independent Study Monitoring Committee (SMC) to the planned team monitoring:

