reduced mineral density may not be completely irreversible and its effect in increased risk of osteoporotic bone fractures later in life is unknown [54]. Currently, bone mass measurement heavily relies on x-ray like DEXA scan which are expensive and not easily accessible in resource limited settings. Development of future assays for biomarkers of bone metabolism for early detection of reduced bone mass will be very useful. The mechanism for the bone loss has not been extensively studied, with very little data in HIV-infected women. Because of this, blood for bone biomarkers will be collected before and 12 weeks after receiving DMPA and future funding for analyses of these specimens will be sought. Of particular interest is the potential additive toxicity of tenofovir disoproxil fumarate (TDF)-containing regimens and other agents that increase bone resorption. This study is not powered to assess this interaction, but evaluation of the cART regimens may lead to the detection of a signal warranting further study.

This study will enroll women with known TB infection during the continuation phase of RIF-containing TB treatment regimen who are on a stable cART regimen consisting of at least 2 NRTIs and EFV. Women will be given DMPA after being on EFV-based cART for at least 4 weeks and on RIF-containing TB treatment for at least 8 weeks. PK assessments for MPA will be assessed pre-dose then every 2 weeks after starting DMPA administration, through week 12. The rationale for giving DMPA at this time point is: (1) RIF and EFV concentrations are near steady state and maximal induction effect will be achieved; and (2) RIF dosing frequency does not change during the continuation phase of TB treatment (whereas frequency and concurrent TB drugs may change between the intensive and the continuation phases). Initiating the study treatment within the four weeks after completion of intensive phase TB treatment allows a 12-week period required for completion of the study.

The results of this study are likely to be applicable to patients receiving RIF-containing TB treatment that are not being treated concurrently with EFV as well, given that addition of EFV to RIF is unlikely to increase induction of metabolizing enzymes significantly beyond the induction achieved with RIF alone.

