4.0 SELECTION AND ENROLLMENT OF SUBJECTS

4.1 Inclusion Criteria

- 4.1.1 HIV-1 infection, documented by any licensed rapid HIV test or HIV enzyme or chemiluminescence immunoassay (E/CIA) test kit at any time prior to study entry and confirmed by a licensed Western blot or a second antibody test by a method

other than the initial rapid HIV and/or E/CIA, or by HIV-1 antigen, plasma HIV-1 RNA viral load.

NOTE: The term “licensed” refers to a US FDA-approved kit, which is required for all IND studies, or for sites located in countries other than the United States, a kit that has been certified or licensed by an oversight body within that country and validated internally. Non-US sites are encouraged to use US FDA-approved methods for IND studies.

WHO and CDC (Centers for Disease Control and Prevention) guidelines mandate that confirmation of the initial test result must use a test that is different from the one used for the initial assessment. A reactive initial rapid test should be confirmed by either another type of rapid assay or an E/CIA that is based on a different antigen preparation and/or different test principle (eg, indirect versus competitive), or a Western blot or a plasma HIV-1 RNA viral load.

4.1.2 Current tuberculosis infection, confirmed or probable diagnosis.

Confirmed TB is defined as:

- demonstration of acid fast bacilli using the Ziehl Nielson or Auramine stain
OR
- a positive culture of *M. tuberculosis* OR
- a positive GeneXpert test in sputum, pleural and pericardial fluid, lymph node aspirate, cerebrospinal fluid or blood.

Probable TB is based on the clinician’s judgment where acid-fast bacilli are not demonstrable but sufficient clinical suspicion exists to initiate empiric TB therapy. A probable diagnosis may be based on the presenting clinical symptoms of fever for more than 2 weeks, unintentional weight loss of more than 10% of body weight, night sweats, positive TB contacts, radiographic findings, and the absence of another possible diagnosis.

4.1.3 Currently stable on EFV-based cART for at least 28 days.

See section 5.1.1 for cART initiation if a woman is not on HIV treatment at the time of screening and acceptable NRTIs.

4.1.4 Currently receiving RIF and Isoniazid (INH)-based TB therapy on at least 5 days per week schedule after completion of the intensive phase of TB treatment (minimum of 8 weeks of TB treatment) and expected to be on TB treatment for a minimum of 12 weeks after enrollment.

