5.1 Regimen, Administration, and Duration

5.1.1 Regimen

At study entry/week 0, participants will receive:

Depot medroxyprogesterone acetate (DMPA) 150 mg administered intramuscularly (IM) as a single-dose.

NOTE: An optional additional dose of DMPA will be provided at no cost to all study participants who successfully complete all 12 weeks of the study, experience no AEs from the first injection, are interested in continuing with DMPA outside of the protocol, and after confirmation of a negative pregnancy test.

Required ARV therapy (not provided through study):

- Efavirenz (EFV) 600 mg orally once daily in combination with 2 or more NRTIs.
- Two or more NRTIs

NOTES:

- a. Acceptable NRTIs include the following:
 - zidovudine (ZDV)
 - lamivudine (3TC)
 - emtricitabine (FTC)
 - didanosine (ddI)
 - stavudine (d4T)
 - abacavir (ABC)
 - tenofovir disoproxil fumarate (TDF)
 - b. Refer to section 5.4.2 for the prohibited NRTI combinations.
- Women who are not already receiving HIV treatment at the time of screening may initiate cART at any time between 2 and 8 weeks after starting TB treatment, at the discretion of the treating physician and health care provider at the local clinic.
 - ARV therapy will not be provided through the study. For participants requiring changes in ARV therapy during the study, see sections 6.2.4 and 8.2 for follow-up and study discontinuation.

Required TB treatment (not provided through study):

- Rifampicin (RIF) 600 mg orally once daily.

- Isoniazid (INH) 300 mg orally once daily.

NOTE: Pyridoxine (vitamin B₆), if recommended by local standard of care with INH, will not be supplied through the study and must be obtained locally by the site.

- Participants must be on the continuation phase of TB treatment with a minimum of 12 weeks of TB treatment remaining.

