6.2 Timing of Evaluations

6.2.1 Screening Evaluations

Screening evaluations must occur prior to the participant's starting any study medications, treatments, or interventions. At the time of screening, participants must have completed the intensive phase and be in the continuation phase of TB treatment. Participants must require at least 12 more weeks of TB treatment at the time they receive the DMPA injection at study entry.

Site staff are encouraged to contact/liaise with primary care physicians at TB clinics for identification of eligible participants prior to completion of the intensive phase of TB treatment. Information about the location of the ARV clinic and planned timing of cART initiation should be obtained. The identified participants will be given appointments for the research clinic as soon as they are initiated on cART. Site staff will obtain contact details of these potential participants to remind them about scheduled screening appointments. Eligible participants will be enrolled as soon as eligibility is determined.

Screening evaluations to determine eligibility must be completed within 30 days prior to study entry unless otherwise specified. In addition to data being collected on participants who enroll into the study, demographic, clinical, and laboratory data on screening failures will be captured in a Screening Failure Results form and entered into the ACTG database.

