6.2.3 Post-Entry Evaluations

Post-entry evaluations occur after study entry and injection of DMPA. Study visits are scheduled as indicated in the Schedule of Events (SOE) in section 6.1. The final visit is the week 12 visit.

The visit windows for post-entry evaluations are ± 3 days for weeks 2, 4, 6, and 8, and ± 7 days for weeks 10 and 12. The evaluations at weeks 10 and 12 should be performed as close as possible to the ideal visit date. If the week 10 or week 12 PK sampling is rescheduled, the reschedule date must be within the original visit window for the visit. There must be at least 3 days between the PK samples collected at each visit.

NOTE: All PK visits must be scheduled to occur following at least 2 consecutive doses of RIF and EFV in those participants who take TB medications <7 days a week.

Participants who elect to receive a second dose of DMPA at week 12 (see section 6.3.11) will have no further follow-up after the second dose of DMPA is administered.

Women who wish to continue receiving DMPA after completing the study will be referred to a family planning program or a program at their local clinic.

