9.2 Outcome Measures

9.2.1 Primary Outcome Measures

MPA concentration levels obtained at 2, 4, 6, 8, 10, and 12 weeks after DMPA is administered. The 12 week measurement will be the measurement obtained closest to 84 days after DMPA is administered. The allowable window for the measurement is ± 7 days, as stated in section 6.2.3.

Plasma progesterone levels obtained at 2, 4, 6, 8, 10, and 12 weeks after DMPA is administered.

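### The 12-week minimum of remaining TB treatment stops at day 84, but the week-12 primary MPA sample may be taken up to day 91, possibly after rifampicin has ended.

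*Protocol*

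**What the plan says.** Three places in the protocol set the minimum remaining TB treatment at 12 weeks. Section 4.1.4 requires that the woman be "expected to be on TB treatment for a minimum of 12 weeks after enrollment". Section 5.1.1 requires the continuation phase "with a minimum of 12 weeks of TB treatment remaining". Section 6.2.1 counts from the injection: "Participants must require at least 12 more weeks of TB treatment at the time they receive the DMPA injection at study entry". The rationale in section 2.2 has the same length in mind; entry within four weeks of the end of the intensive phase "allows a 12-week period required for completion of the study".

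The sampling rules run longer. Section 9.2.1 states: "The 12 week measurement will be the measurement obtained closest to 84 days after DMPA is administered", with a window of 7 days either side, so days 77 to 91 are permitted. Section 6.2.3 adds: "If the week 10 or week 12 PK sampling is rescheduled, the reschedule date must be within the original visit window for the visit". Section 10.2, as revised by Letter of Amendment #1, moves a visit that fails the adherence check to one week later, within that window.

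The adherence rule for these visits is section 8.1.4, also revised by Letter of Amendment #1. It applies to a woman who has "Missed 2 or more of the RIF and/or EFV doses within one week prior to PK sampling at week 10 or 12" and who again lacks acceptable adherence at the rescheduled sample. Such a woman leaves the study and is replaced.

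**The concern.** Eligibility secures rifampicin only to day 84, while a valid primary sample can be drawn up to 7 days later. For a woman at the minimum, the second half of the window may fall after her last dose. The plan treats two or more missed doses in the prior week as unacceptable for PK sampling, so it regards that much time off the drug as relevant to the measurement.

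Two things are at stake. The first is who enters the primary analysis: sites could differ on whether a completed course counts as missed doses. The second is what the week-12 value measures: a sample taken off rifampicin no longer reflects the co-administration under study. The primary cut-off is 6 women of 42, so individual classifications matter.

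**Working it through.** **The plan's own figure.** Section 9.4 uses a one-sided exact binomial test at 0.05, null 6%, alternative 21%, n = 42, rejecting at 6 or more.

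- P(X ≥ 6 | n = 42, p = 0.06) = 0.0382.
- P(X ≥ 6 | n = 42, p = 0.21) = 0.9009.
- The lower limit of the 90% Clopper-Pearson interval is 6.41% at 6/42 and 4.81% at 5/42.

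The stated 90% power and the cut-off of 6 both reproduce.

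**The dates.** Count the injection as day 0.

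- Minimum remaining treatment: 12 × 7 = 84 days.
- Latest permitted week-12 sample: 84 + 7 = day 91.
- Gap: 91 − 84 = 7 days.

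**Rifampicin-free days in the week before sampling.** For a sample on day s, the prior week is days s − 7 to s − 1. If the last dose is on day L, the count of rifampicin-free days is max(0, s − 1 − L), up to 7. With daily dosing, a course ending at exactly 12 weeks has L = 83 or L = 84, depending on how the days are counted.

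| Sampling day | L = 83 | L = 84 |
|---|---|---|
| 77 to 84 | 0 | 0 |
| 85 | 1 | 0 |
| 86 | 2 | 1 |
| 87 | 3 | 2 |
| 88 | 4 | 3 |
| 89 | 5 | 4 |
| 90 | 6 | 5 |
| 91 | 7 | 6 |

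The count reaches 2 on day 86 or day 87, that is, on 6 or 5 of the 15 window days. On a 5-day schedule, 2 scheduled doses are absent from somewhere between day 86 and day 89, and 4 or 5 are absent at day 91.

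**The rescheduling rule.** A woman at the minimum who fails the adherence check on day 84 is moved to 84 + 7 = day 91. By then she has had 6 or 7 rifampicin-free days, so the repeat visit cannot show restored dosing.

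**Could women be at the minimum?** Sections 3.0 and 5.1.1 let cART start up to 8 weeks after TB treatment begins, and section 4.1.3 requires 28 days of EFV-based cART. A woman starting at week 8 is first eligible at 8 + 4 = week 12 of TB treatment. After an 8-week intensive phase, that is the end of the four-week entry period in section 2.2. If 12 weeks remain at that point, as section 2.2 implies, she sits on the boundary.

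**What the documents leave open.** Section 8.1.4 does not define missed doses after a completed course. Section 8.2.2 lists stopping rifampicin only for toxicity or resistance. Section 9.6.1 analyses women who complete the week-12 PK sampling and has no rule for samples taken off rifampicin. The SAP addresses only objectives 1.3.1 and 1.3.2 and adds none.

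**The case against.** A reader might infer that a woman who finishes rifampicin on time will be discontinued and replaced as non-compliant. The documents do not support that. Section 8.1.4 concerns missed doses under a noncompliance heading, and nothing there counts days after a completed course as missed. It also needs a second failure at the rescheduled sample. A woman who takes rifampicin through day 84 and attends by day 84 is not affected by completion at all. The route from day 84 to day 91 begins with doses really missed earlier. This objection stands: discontinuation is one open reading, not a stated consequence.

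Existing provisions also narrow the gap. Section 6.2.3 asks for week 12 as close as possible to the ideal date. It also requires at least 2 consecutive rifampicin and EFV doses before a PK visit for women dosed fewer than 7 days a week, which on its face bars a visit after rifampicin has ended. Section 4.1.4 sets an expected minimum, and section 6.2.1 favours enrolment as soon as eligibility is determined, so many women may have more than 12 weeks left. All of this limits the exposure. It does not remove it: the timing request is a preference, and the two-dose note does not cover women dosed daily.

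A reader might also infer a loss of power. Women discontinued for noncompliance are replaced. Even without replacement, suppose for illustration that 1 or 2 of the 46 enrolled were lost. That leaves 45 or 44. Taking the smallest cut-off with level at most 0.05, power is 0.877 at 46 (cut-off 7), 0.862 at 45 (cut-off 7) and 0.923 at 44 (cut-off 6). These differences mainly reflect the step in the cut-off, and they show no consistent loss against the planned 0.901.

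Finally, the documents give no rate at which induction wears off, so bias from a few rifampicin-free days is possible but not quantified.

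**Conclusion.** The mismatch is real and minor. The 12-week minimum falls 7 days short of the last permitted week-12 sampling day. A woman on a daily course at that minimum can be sampled within the window with 2 or more rifampicin-free days in the prior week from day 86 or 87, and 6 or 7 by day 91. The protocol does not settle whether she then falls under section 8.1.4 or her sample is kept.

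This rests on a course that ends at, or within a few days of, 12 weeks after entry and on a late or rescheduled week-12 visit. The documents do not say how many women meet both conditions. The planned sample size and power are not called into question.

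**What to change.** Reconcile sections 4.1.4, 5.1.1 and 6.2.1 with sections 6.2.3, 9.2.1, 8.1.4 and 10.2, so that every permitted week-12 PK sampling day falls while the woman is still on rifampicin. One way is to close her week-12 sampling window at the end of her scheduled course. The sponsor should also state how planned completion of the course is treated for section 8.1.4 and for evaluability in the primary analysis. Which treatment applies is for the sponsor to decide.

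The cost is wording in a letter of amendment, the route already used to clarify these rules, and a slightly narrower week-12 window for some women. No change to TB treatment is implied.

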4.1.10 Women between the ages of 18 to 46 years

4.1.11 Ability and willingness to provide written informed consent

4.2 Exclusion Criteria

4.2.1 Receipt of DMPA and any other injectable contraceptives within 180 days prior to study entry.

- 4.2.2 Receipt of other hormonal contraceptives within 30 days prior to study entry.
- 4.2.3 Use of any drugs other than RIF and EFV known to: 1) induce CYP3A4 system within 30 days and to 2) inhibit the CYP3A4 system with one week prior to study entry.
- 4.2.4 ≤ 40 kg in weight.
- 4.2.5 Bilateral oophorectomy.
- 4.2.6 Less than 30 days postpartum at study entry.
- 4.2.7 Hypersensitivity to DMPA, MPA, or any of the other ingredients in DMPA.
- 4.2.8 Breast cancer.
- 4.2.9 Serious illness requiring systemic treatment and/or hospitalization within 21 days prior to study entry.
- 4.2.10 Karnofsky performance score < 70 within 14 days prior to study entry.
- 4.2.11 Use of any immunosuppressant medication including systemic corticosteroids within 30 days prior to study entry.

NOTE: Use of systemic or inhaled corticosteroids, such as for acute therapy for *Pneumocystis jirovecii* pneumonia (previously called *Pneumocystis carinii* pneumonia; PCP) or asthma exacerbation or TB Immune Reconstitution Inflammatory Syndrome (IRIS), and prednisone ≤ 10 mg (or equivalent) is permitted as a stable or tapering dose.

- 4.2.12 Active drug or alcohol use or dependence that, in the opinion of the site investigator, would interfere with adherence to study requirements.
 - 4.2.13 History of deep venous thrombosis or pulmonary emboli.
- 4.3 Study Enrollment Procedures
- 4.3.1 Prior to implementation of this protocol, and any subsequent full version amendments, each site must have the protocol and the protocol consent form(s) approved, as appropriate, by their local institutional review board (IRB)/ethics committee (EC) and any other applicable regulatory entity (RE). Upon receiving final approval, sites will submit all required protocol registration documents to the DAIDS Protocol Registration Office (DAIDS PRO) at the Regulatory Support Center (RSC). The DAIDS PRO will review the submitted protocol registration packet to ensure that all of the required documents have been received.

Site-specific informed consent forms (ICFs) WILL be reviewed and approved by the DAIDS PRO, and sites will receive an Initial Registration Notification from the

DAIDS PRO that indicates successful completion of the protocol registration process. A copy of the Initial Registration Notification should be retained in the site's regulatory files.

Upon receiving final IRB/EC and any other applicable RE approvals for an amendment, sites should implement the amendment immediately. Sites are required to submit an amendment registration packet to the DAIDS PRO at the RSC. The DAIDS PRO will review the submitted protocol registration packet to ensure that all the required documents have been received. Site-specific ICF(s) WILL NOT be reviewed and approved by the DAIDS PRO, and sites will receive an Amendment Registration Notification when the DAIDS PRO receives a complete registration packet. A copy of the Amendment Registration Notification should be retained in the site's regulatory files.

For additional information on the protocol registration process and specific documents required for initial and amendment registrations, refer to the current version of the DAIDS Protocol Registration Manual.

Once a candidate for study entry has been identified, details will be carefully discussed with the participant. The participant will be asked to read and sign the approved protocol consent form.

For participants from whom a signed informed consent has been obtained, an ACTG Screening Checklist must be entered through the Data Management Center (DMC) Subject Enrollment System.

4.3.2 Participant Registration

For participants from whom informed consent has been obtained, but who are deemed ineligible or who do not enroll into the initial protocol step, an ACTG Screening Failure Results form must be completed and keyed into the database. At entry, participants will be registered according to standard ACTG DMC procedures.

